
IV (or iv) Intravenously

NCI National Cancer Institute
ORR Overall Response Rate

OS Overall Survival

PD Progressive Disease

PFS Progression Free Survival

[figure not shown]
PR Partial Response

SAE Serious Adverse Event

SD Stable Disease

÷

STUDY SCHEMA

STUDY SUMMARY

Abbreviated Title	Pembrolizumab plus olaparib in advanced BRCA-mutated or HDR-defect breast cancer	
Trial Phase	II	
Clinical Indication	Therapy for metastatic disease after progression on at least one line of prior therapy	
Trial Type	Pilot Study - Open label phase II	
Type of control	N/A	
Route of administration	Intravenous infusion (pembrolizumab), oral (olaparib)	
Trial Blinding	N/A	
Treatment Groups	Advanced breast cancer with BRCA germline or somatic mutation or HDR-defect	
Number of trial subjects	20 (pilot study)	
Estimated Enrollment Period	36 months	
Estimated duration of trial	42 months	
Duration of Participation	2-24 months	
Main Eligibility Criterion	Female and Male patients with advanced BRCA-mutated or HDR-defect breast cancer progressing on or after prior therapy for metastatic disease or locally advanced disease; Prior therapy is defined as follows: for triple negative breast cancer – progressing after at least 1 line of any prior chemotherapy; for HER2 positive disease must have progressed after at least two HER2 directed therapies in the metastatic setting including ado-trastuzumab emtansine (T-DM1); for hormone receptor positive disease (ER, PR, or both) must have progressed after a CDK4/CDK6 inhibitor plus hormonal therapy. Patients with progression within 12 months from previous neoadjuvant or adjuvant treatment could be enrolled in the study as 1st line therapy in metastatic setting.	

1.0 BACKGROUND AND RATIONALE

1.1 Disease Background

Breast cancer due to germline BRCA 1 or BRCA2 mutation represents approximately 5-10% of the breast cancer population. BRCA 1 and 2 germline mutations are readily determined through commercially available testing of blood and buccal cell DNA. While all breast cancer molecular subtypes may occur in BRCA mutation carriers, it is recognized that approximately 70% of breast cancers developing in BRCA 1 carriers are likely to be triple negative, while over 50% of breast cancer developing in BRCA 2 carriers are estrogen receptor positive. HER2 positive breast cancers may also occur with either BRCA 1 or BRCA2 mutations at a frequency of 10-13% [1]. Historically, breast cancer in BRCA mutation carriers has not been treated differently than breast cancer occurring "sporadically", according to standard of care guidelines [2, 3]. An inhibitor of the poly (ADP) ribose polymerase (PARP) 1 enzyme, olaparib[4], has been FDA-approved for use in BRCA-mutated ovarian cancer, and clinical trials were recently conducted with these compounds in breast cancer [5]. In 2018, the FDA approved olaparib for germline BRCA-mutated metastatic breast cancer [21]. Response rates with PARP inhibitors in BRCA-mutated breast cancer have ranged from 0 to 41%, with a median progression free survival of 6 months [6, 7]. There remains a significant unmet need for therapy with specific benefit in BRCA-mutated breast cancer. Immunotherapy may offer a targeted therapy with less toxicity than chemotherapy, and potentially greater efficacy for this population with an unmet need for targeted therapy approaches. Positive results in this cohort would be of major clinical research interest and benefit to this population.

The histopathology of BRCA-associated breast cancer suggests a role for the immune system in BRCA biology, based on several observations. Lymphocytic infiltrates are pathognomonic of medullary carcinoma of the breast, a subtype highly associated with BRCA 1 mutation, and lymphocytic infiltrates are commonly noted in BRCA-mutated cancers [8]. More recently the role of the immune system, tumor infiltrating lymphocytes (TILs), and the PD-1/PDL-1 pathway has been studied in breast cancer in general [9]. Of 116 breast cancers, 45% expressed PDL-1, with variation by molecular profile: 59% of triple negative, 33% of estrogen positive and 20% of HER2 positive breast cancers expressed PDL-1. TILs expressing PD-1 were also observed, with the highest proportion having concurrent expression of PD-1 TILs and PDL-1 tumor cells (45%) seen in triple negative breast cancer (TNBC). The only reported analysis of PDL-1 expression in BRCA mutated breast cancer to date indicated in a small subset of triple negative breast cancers, a significant correlation of PD-L1 and BRCA germline mutation, with 7 of 7 BRCA1 mutated breast cancers overexpressing PD-L1[10].

Additional data regarding the expression of PDL-1 in BRCA-mutated cancers have been obtained through a study in collaboration with Merck and Cedars-Sinai Medical Center, for which [name] was the PI [11]. A cohort of 30 primary breast cancer tumor samples obtained prior to treatment from germline BRCA mutation carriers (identified previously by genetic testing) were identified within the Cedars-Sinai Pathology Department and were analyzed for relevant immune biomarkers through collaboration with Merck, The laboratory project, funded by Merck, assessed the expression of immune biomarkers PDL-1 and PD-1 using Merck-developed antibodies. The results of the study were as follows: Twenty (20) tumors were from BRCA 1 mutations carriers, and 10 were BRCA2, Sixteen (16) were basal type breast cancer (13 BRCA1, 3 BRCA2), 14 were estrogen receptor positive(ER+)(7 BRCA1, 7BRCA2), with 7 Luminal A and 7 Luminal B. There were no HER2 amplified tumors in the cohort. PD1 expression was observed in 11/30 (37%) of the cohort, and PDL1 expression was detected in 21/30 (70%) of the cohort. PDL1 expression was seen in 15/20 (75%) of tumors from BRCA1 mutation carriers, and 6/10 (60%) of tumors from BRCA2 carriers. PDL1 expression was present in 13/16 (81%) basal tumors and 8/14 (57%) ER+ tumors. Within the cohort of PDL1 expressing cancers. 7/21 (33%) were scored as "high" or "very high", 5 basal breast cancers and 2 ER+ cancers. The study therefore identified a high rate of PDL1 expression in untreated primary breast cancers with germline BRCA1 and BRCA2 mutations, regardless of intrinsic subtype. PDL-1 expression, in association with other relevant biomarkers, in BRCA-mutated cancers may predict a dependence

on immune suppression for tumor survival, and may predict responsiveness to immune checkpoint inhibition with pembrolizumab.

Evaluation of targeted therapy specific to the biology of BRCA-mutated cancers has been limited to the use of PARP inhibition, which acts through the mechanism of "synthetic lethality", inducing additional DNA damage and cytotoxicity in cells with homologous repair defects (HRD), and which produces a variety of dose-limiting toxicities, primarily hematologic.

Immunotherapy may offer a targeted therapy with less toxicity, and potentially greater efficacy for this population with an unmet need for targeted therapy approaches. Positive results in this cohort would be of major clinical research interest and benefit to this population.

Combining PARP inhibitors and immunotherapy is a current treatment tested in several studies and tumor types. Rationale derives from the observation that PARP inhibitors enhanced cancer's ability to produce PD-L1 which enhances the efficacy of immunotherapy (Pd-1 and PDL1 inhibitors). In clinical studies tolerability of the combination is very good with no overlapping toxicities [25-28]. Due to evidence of combinatorial efficacy with the combination, patients previously exposed to PARP inhibitors will remain eligible as the patients PARP inhibitors naïve.

Patients with ER+ disease benefit from continuous hormonal inhibition. Studies show that combination therapy with PARP inhibition and anti-estrogens is safe and there are no interactions [29-30]. Therefore, this study will allow continuation of anti-estrogen therapy for patients with ER+ disease. While there is pre-clinical data on the combination of PARP inhibition and trastuzumab antitumor activity in HER2+ disease [31], due to a lack of safety data, subjects with HER2+ disease will be required to discontinue trastuzumab therapy.

1.2 Study Agent(s) Background and Associated Known Toxicities

1.2.1 Pembrolizumab

The importance of intact immune surveillance in controlling outgrowth of neoplastic transformation has been known for decades [32]. Accumulating evidence shows a correlation between tumor-infiltrating lymphocytes (TILs) in cancer tissue and favorable prognosis in various malignancies. In particular, the presence of CD8+ T-cells and the ratio of CD8+ effector T-cells / FoxP3+ regulatory T-cells (T-regs) correlates with improved prognosis and long-term survival in many solid malignancies, such as ovarian, colorectal, and pancreatic cancer; hepatocellular carcinoma; malignant melanoma; and renal cell carcinoma. Tumor-infiltrating lymphocytes can be expanded ex vivo and reinfused, inducing durable objective tumor responses in cancers such as melanoma [33-34].

The PD-1 receptor-ligand interaction is a major pathway hijacked by tumors to suppress immune control. The normal function of PD-1, expressed on the cell surface of activated T-cells under healthy conditions, is to down-modulate unwanted or excessive immune responses, including autoimmune reactions. PD-1 (encoded by the gene Pdcd1) is an Ig superfamily member related to CD28 and CTLA-4 which has been shown to negatively regulate antigen receptor signaling upon engagement of its ligands (PD-L1 and/or PD L2) [35-36].

The structure of murine PD-1 has been resolved [37]. PD-1 and family members are type I transmembrane glycoproteins containing an Ig Variable-type (V-type) domain responsible for ligand binding and a cytoplasmic tail which is responsible for the binding of signaling molecules. The cytoplasmic tail of PD-1 contains 2 tyrosine-based signaling motifs, an immunoreceptor tyrosine-based inhibition motif (ITIM) and an immunoreceptor tyrosine-based switch motif (ITSM). Following T-cell stimulation, PD 1 recruits the tyrosine phosphatases SHP-1 and SHP-2 to the ITSM motif within its cytoplasmic tail, leading to the dephosphorylation of effector molecules such as CD3 ζ , PKC θ and ZAP70 which are involved in the CD3 T-cell signaling cascade [36; 38-40]. The mechanism by which PD-1 down modulates T-cell responses is similar to, but distinct from that of CTLA-4 as both molecules regulate an overlapping set of signaling proteins [41-42]. As a

consequence, the PD 1/PD-L1 pathway is an attractive target for therapeutic intervention in breast cancer.

Pembrolizumab is a potent humanized immunoglobulin G4 (IgG4) monoclonal antibody (mAb) with high specificity of binding to the programmed cell death 1 (PD 1) receptor, thus inhibiting its interaction with programmed cell death ligand 1 (PD-L1) and programmed cell death ligand 2 (PD-L2). Based on preclinical in vitro data, pembrolizumab has high affinity and potent receptor blocking activity for PD 1. Pembrolizumab has an acceptable preclinical safety profile and is in clinical development as an intravenous (IV) immunotherapy for advanced malignancies. Keytruda® (pembrolizumab) is indicated for the treatment of patients across a number of indications because of its mechanism of action to bind the PD-1 receptor on the T cell. For more details on specific indications refer to the Investigator brochure.

Refer to the Investigator's Brochure for Preclinical and Clinical data.

1.2.2 Olaparib

Investigators should be familiar with the current olaparib package insert.

Olaparib (AZD2281, KU-0059436) is a potent Polyadenosine 5'diphosphoribose [poly (ADP ribose)] polymerisation (PARP) inhibitor (PARP-1, -2 and -3) that is being developed as an oral therapy, both as a monotherapy (including maintenance) and for combination with chemotherapy and other anti-cancer agents.

PARP inhibition is a novel approach to targeting tumours with deficiencies in DNA repair mechanisms. PARP enzymes are essential for repairing DNA single strand breaks (SSBs). Inhibiting PARPs leads to the persistence of SSBs, which are then converted to the more serious DNA double strand breaks (DSBs) during the process of DNA replication. During the process of cell division, DSBs can be efficiently repaired in normal cells by homologous recombination repair (HR). Tumours with HR deficiencies (HRD), such as ovarian cancers in patients with BRCA1/2 mutations, cannot accurately repair the DNA damage, which may become lethal to cells as it accumulates. In such tumour types, olaparib may offer a potentially efficacious and less toxic cancer treatment compared with currently available chemotherapy regimens.

BRCA1 and BRCA2 defective tumours are intrinsically sensitive to PARP inhibitors, both in tumour models in vivo [43-44] and in the clinic [45]. The mechanism of action for olaparib results from the trapping of inactive PARP onto the single-strand breaks preventing their repair [46-47]. Persistence of SSBs during DNA replication results in their conversion into the more serious DNA DSBs that would normally be repaired by HR repair. Olaparib has been shown to inhibit selected tumour cell lines in vitro and in xenograft and primary explant models as well as in genetic BRCA knock-out models, either as a stand-alone treatment or in combination with established chemotherapies.

Tumors with HDR-defect (homology-related repair) have the same propensity to be sensitive to PARP inhibitors as the BRCA mutated tumors. This has been demonstrated in several studies and mechanistically explained [22-24]. Two clinical studies, reported recently have confirmed antitumor activity with PARP inhibitors in tumors with HRD defect (but not necessary BRCA mutated). First study (TBCRC 048) published in JCO 2020 by N Tung presented responses to different somatic and germline mutations with PARP inhibitors treatment. Similar responses were seen in the somatic vs germline cohort in BRCA and other HRD defects tumors. A second study SWOG 1416 presented at ASCO 2020 revealed that addition of a PARP inhibitor, in this case Veliparib to chemotherapy in BRCA like triple negative metastatic breast cancer patients has similar efficacy compared to BRCA population.

1.3 Tempus HRD

The Tempus HRD detection approach is a model used in conjunction with data from the Tempus|xT Solid Tumor + Normal test, a 648- gene NGS panel spanning 3.6 Mb of DNA. Therefore, if a physician orders xT to identify actionable mutations in their patient's tumor, no additional tissue is required to process an HRD status. The laboratory developed test is performed using Tempus DNA sequencing data to determine deleterious BRCA1/2 mutations, BRCA1/2-specific LOH, and somatic GW LOH, culminating in an HRD score that indicates each patient's likelihood for PARPi response. Additionally, the Tempus HRD report includes results from a variant assessment of 16 other HR-related genes (18 total) conducted as part of the xT testing.

1.4 Rationale

The proposed trial will evaluate the use of immunotherapy in a population with incurable advanced breast cancer associated with a germline or somatic BRCA mutation or HDR-defect, in combination with targeted therapy with olaparib. The genomic instability of BRCA-mutated breast cancer suggests probable increased neoantigen production and antigenicity, and predicts a dependence on immune suppression for carcinogenesis and tumor growth.

Blockade of the inhibitory immune checkpoint controlled by programmed cell death protein 1 (PD-1) and its ligand (PDL-1) has produced clinical responses in a number of malignancies, most significantly melanoma, non-small cell carcinoma, renal cell carcinoma[12] [13]and ovarian cancer [14]. In breast cancer, preliminary data from a phase lb trial of 32 women with TNBC treated with pembrolizumab at 10mg/kg every 2 weeks yielded a response rate of 18.5%[15]. Biomarkers for response to PD-1 directed therapy may be PDL-1 overexpression[16] [17], as well as possibly other histologic and genomic features. Genomically, the tumors in which responses were seen (melanoma, NSCLC, RCC and TNBC) are also known to have a high degree of genomic instability and mutational load relative to other malignancies [18]. A high mutation rate is likely to produce neoantigens, to which an immune response would be generated, and would be expected to produce evolutionary selection pressure favoring tumors which are able to block the resulting immune response. Therefore, it is hypothesized that genomically unstable tumors may be more likely to utilize inhibition of the immune response through upregulation of PDL-1.

Tumors characterized by intrinsic genomic instability and high mutational load include those with mismatch repair (MMR) defects and those with homologous recombination defects due to BRCA 1 or 2 gene germline mutations. The present study proposes a proof of concept trial in BRCA-mutated breast cancers.

Similar to the previously observed pembrolizumab-responsive tumors, BRCA-mutated cancers are known to be highly genomically unstable[19] [20] and are also characterized histologically by robust lymphocytic infiltrates. It is hypothesized that the genomic instability and high mutation rate in BRCA-mutated cancers results in neoantigens, eliciting a host immune response and selecting for mechanisms for immune escape, such as PDL-1 overexpression.

Little is known regarding the role of the immune system checkpoints in BRCA-mutated cancers, however, data presented at ASCO 2014 by Pockaj et al [10]suggested a high degree of correlation of PD-L1 with lack of BRCA expression, with 7 of 7 BRCA 1 mutated breast cancers overexpressing PD-L1. Data from the Merck/Cedars-Sinai BRCA collaboration in which 30 BRCA-mutated cancers were analyzed indicated a high frequency of PDL-1 expression in BRCA mutated breast cancer.

Based on the observation that genomically unstable malignancies have shown responses to pembrolizumab, the association of PDL-1 expression with likelihood of response, and the preliminary data suggesting a high rate of PDL-1 expression in BRCA-mutated breast cancer, the

trial will evaluate the use of pembrolizumab in addition to olaparib in a population with incurable, advanced breast cancer associated with a germline or somatic BRCA mutation. The genomic instability of BRCA-mutated breast cancer suggests probable increased neoantigen production and antigenicity, and predicts a dependence on immune suppression for carcinogenesis and tumor growth.

2.0 STUDY OBJECTIVES

2.1 Primary Objective

Overall Response Rate (ORR) of pembrolizumab therapy in addition to olaparib therapy in advanced BRCA-mutated or HDR-defect breast cancer, as measured by RECIST 1.1, in patients progressing after prior therapy.

2.2 Secondary Objectives

- **2.2.1** Progression Free Survival (PFS), as measured by RECIST 1.1, in patients progressing after prior therapy from baseline to the date of the first evidence of progression for up to two years.
- **2.2.2** Overall survival (OS), from baseline until death for up to two years.
- **2.2.3** Clinical Benefit Rate (CR+PR+SD), as measured by RECIST 1.1, in patients progressing after prior therapy from baseline for up to two years.
- **2.2.4** Duration of Response (DOR) for CR and PR, as measured by RECIST 1.1, in patients progressing after prior therapy from baseline for up to two years.

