4.3 Concomitant Medications/Treatments

4.3.1 Acceptable Concomitant Medications

All treatments that the investigator considers necessary for a subject's welfare may be administered at the discretion of the investigator in keeping with the community standards of medical care. The use of any natural/herbal products or other traditional remedies should be discouraged, but use of these products, as well as any medication or vaccine including over-the-

counter or prescription medicines, vitamins, and/or herbal supplements that the patient is receiving at the time of enrolment or receives during the study must be recorded along with reason for use, dates of administration including start and end dates, dosage information including dose and frequency. If changes occur during the trial period, documentation of drug dosage, frequency, route, and date will also be included on the CRF.

Anti-emetics/Anti-diarrhoeals

Should a patient develop nausea, vomiting and / or diarrhoea, then these symptoms should be reported as AEs (see section 8.3) and appropriate treatment of the event given.

Subjects with ER+/PR+ disease may be given endocrine therapy.

Specifically, subjects using bisphosphonates or anti-RANKL mAb who were receiving this medication prior to study start, may continue receiving the medication during the study. However, a need to initiate this therapy during the conduct of this trial will be the equivalent of clinical disease progression and the subject must discontinue study treatment.

All concomitant medications received within 30 days before the first dose of pembrolizumab through the Safety Follow-up Visit should be recorded. After the Safety Follow-up Visit record all medications taken for SAEs and ECIs as defined in Section 6.3.2.

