4.3.2 Prohibited Concomitant Medications

Subjects are prohibited from receiving the following therapies during the Screening, Treatment and Second Course Phases of this trial (unless otherwise noted below):

- Antineoplastic systemic chemotherapy or biological therapy not specified in this protocol.
- Immunotherapy not specified in this protocol
 - Subjects with HER2+ disease will be required to discontinue trastuzumab (Herceptin).
- Chemotherapy not specified in this protocol
- Investigational agents other than pembrolizumab
- Non-palliative radiation therapy (radiation that's considered palliative in nature as determined by treating investigator is allowed).
- Live vaccines or live-attenuated vaccines within 30 days prior to the first dose of pembrolizumab and while participating in the trial. Administration of killed vaccines is allowed.
- Initiation of bisphosphonate or anti-RANKL mAb (Treatment and Second Course Phases).

Subjects who, in the assessment by the investigator, require the use of any of the aforementioned treatments for clinical management should be removed from the trial. Subjects may receive other medications that the investigator deems to be medically necessary.

Restricted concomitant medications

Medication/class of drug:	Usage (including limits for duration permitted and special situations in which it's allowed):

Restricted concomitant medications

Usage (including limits for duration permitted and Medication/class of drug: special situations in which it's allowed):

Strong CYP3A inhibitors: itraconazole, telithromycin, clarithromycin, boosted protease inhibitors, indinavir, saquinavir, nelfinavir, boceprevir, telaprevir

Moderate CYP3A inhibitors: ciprofloxacin, erythromycin, diltiazem, fluconazole, verapamil

Strong or moderate CYP3A inhibitors should not be taken with olaparib. If there is no

suitable alternative concomitant medication then the dose of *olaparib* should be reduced for the period of concomitant administration. The dose reduction of olaparib should be recorded in the CRF with the reason documented as concomitant CYP3A inhibitor

- Strong CYP3A inhibitors reduce the dose of olaparib to 100 mg twice daily for the duration of concomitant therapy with the strong inhibitor and for 5 half lives afterwards.
- Moderate CYP3A inhibitors reduce the dose of olaparib to 150 mg twice daily for the duration of concomitant therapy with the moderate inhibitor and for 3 half lives afterwards.

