4.5 Duration of Therapy

Patients will continue with pembrolizumab until disease progression or unacceptable toxicity, or until completion of 35 treatments of pembrolizumab (approximately 2 years), as long as in the Investigator's opinion they are benefiting from treatment and they do not meet any other discontinuation criteria. Once patients have been discontinued from study treatment, other treatment options (including compassionate use) will be at the discretion of the investigator. Subjects will receive olaparib according to the FDA approved package insert until disease progression or unacceptable toxicity.

In patients with initial disease progression substantiated by radiographic imaging per RECIST 1.1, study treatment may continue until repeat imaging is conducted, at least 4 weeks and no later than 8 weeks later, under the following conditions:

- No worsening of ECOG Performance Status
- No clinically relevant increases in disease-related symptoms thought to be associated with disease progression
- No requirement for intensified management of disease-related symptoms exists, including increased analgesia, radiotherapy, or other palliative care.

Disease progression can also be confirmed histologically, cytologically, or surgically, or by physical examination or other clinical signs, per PI discretion.

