4.6 Duration of Follow Up

Primary and secondary response objectives will be met with approximately 1 month end of study follow-up for subjects discontinuing therapy due to progression. Subjects who discontinue trial treatment for a reason other than disease progression will move into the Follow-Up Phase and should be assessed every 12 weeks (56 ± 7 days) by radiologic imaging to monitor disease status, per standard of care for up to two years of total study participation. Every effort should be made to collect information regarding disease status until the start of new anti-neoplastic therapy, disease progression, death, or at end of the study.

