5.15 Time and Events Table

	Screening				End of Treatment ⁴	SOC Follow- up ⁵								
Procedure	(Within 6 weeks of Day 1)	C1 D1	C1 D8	C1 D15	C2 D1	C2 D8	C3 D1	C4 D1	C5 D1	C6 D1	Even Cycles	Odd Cycles	30-days after drug discontinuation, +/- 7 days	Every 12 Weeks
Informed Consent ¹	Х													
Tempus HRD ¹¹	Х													
Physical Exam (includes Medical history)	х	х	х	х	х		х	х	х	х	X	×	Х	Х
Vitals ²	Х	Х	Х	Х	Х		Х	Х	Х	Х	Х	Х	Х	Х
ECOG Performance Status	х	х			Х		Х	Х	Х	Х	Х	Х	Х	Х
Hematology ⁸	Х	Х	Х	Х	Х	Х	Х	Х	Х	Х	Х	Х	Х	Х
Chemistry ⁸	Х	Х	Х	Х	Х	Х	Х	Х	Х	Х	Х	Х	Х	Х
Tumor markers (CA2729, CEA, CA- 125)		as per standard of care, at the investigator's discretion												
T3 Free, T4 Free, TSH ⁸	Х				Х			Х		Х	Х		Х	
Coagulation (PT, INR, aPTT)	X ⁸													
Urine or serum pregnancy test	X ₈													
EKG	Х													
Archival Tumor Tissue Collection	X ¹⁰													
CT Scan (Chest, Abdomen, Pelvis) and/or MRI	×		As clinically indicated (or every 9 weeks for Response assessment)						Х					
Whole body Bone Scan	Х		As clinically indicated											

Procedure	Screening (Within 6 weeks of Day 1)	Treatment Phase (+/- 3 days) ³											End of Treatment ⁴	SOC Follow- up ⁵
		C1 D1	C1 D8	C1 D15	C2 D1	C2 D8	C3 D1	C4 D1	C5 D1	C6 D1	Even Cycles	Odd Cycles	30-days after drug discontinuation, +/- 7 days	Every 12 Weeks
Adverse Event Assessment	Х		Х	Х	X		Х	Х	Х	Х	х	Х	Xe	X ⁶
Concomitant Medications	Х		Х	Х	X		Х	Х	Х	Х	Х	Х	Х	Х
Pembrolizu mab Administrati on		x			х		х	х	х	Х	Х	Х		
Olaparib Administrati on and Olaparib Compliance Diary			Daily ⁷											

¹Informed consent may be obtained within 6 weeks of Cycle 1, Day 1

²Vital signs to include temperature, pulse, respiratory rate, weight, and blood pressure. Height will be measured at Screening only.

³Study treatment is up to 35 administrations of pembrolizumab (approximately two years).

⁴If subject discontinues drug due to progression, the End of Treatment visit (30 days after study treatment discontinuation, +/- 7 days) will end their participation in the study and will not be followed thereafter.

⁵Subjects who discontinue trial treatment for a reason other than disease progression will move into the Follow-Up Phase and should be assessed every 12 weeks (56 ± 7 days) by radiologic imaging to monitor disease status, per standard of care for up to two years of total study participation.

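### Section 2.2.1 leaves death out of PFS, so applied literally it estimates time to RECIST progression and overstates PFS whenever a patient dies without one

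*Combined protocol and SAP*

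**What the plan says.** Section 2.2.1 sets PFS as a secondary objective, measured by RECIST 1.1, "from baseline to the date of the first evidence of progression for up to two years". Death is not mentioned. The next item, 2.2.2, does name it: "Overall survival (OS), from baseline until death for up to two years". Section 9.3.2 says that time-to-event outcomes will be estimated by Kaplan-Meier, compared by log-rank and modelled by Cox regression. It does not say what counts as a PFS event or when a patient is censored, and no other section does.

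The protocol also recognises one kind of progression that need not be a RECIST progression. Under section 4.3.1, a need to start a bisphosphonate or an anti-RANKL antibody "will be the equivalent of clinical disease progression and the subject must discontinue study treatment". Section 4.3.2 lists starting such an agent among the prohibited therapies, and patients who "require the use of any of the aforementioned treatments for clinical management should be removed from the trial".

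For a patient who stops because of progression, footnote 4 of section 5.15 says that the 30-day End of Treatment visit "will end their participation in the study and will not be followed thereafter". Patients who stop for other reasons have disease status collected under section 4.6 "until the start of new anti-neoplastic therapy, disease progression, death, or at end of the study".

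Section 4.8 makes patients with less than 6 weeks of study treatment non-evaluable for efficacy and replaces them.

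**The concern.** An endpoint that ends only at progression is time to progression, whatever its label. Under Kaplan-Meier, a patient who dies with no RECIST progression would then be censored, as if the patient might still progress later. That censoring is informative, because the patient left the risk set through the worst outcome.

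The bone-agent rule can have a similar effect. The patient is treated as having progressed and leaves the study, but the PFS definition recognises only RECIST progression and no later scan is scheduled to supply one.

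At stake is the reading of PFS in an uncontrolled trial of 20 patients, where one or two uncounted failures can matter. Two analysts could also draw different curves from the same data, because the plan does not say which events count.

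**Working it through.** The plan states no PFS figure, so there is none to reproduce. Its only design calculation is the Simon design in section 9.2, which concerns clinical benefit and does not use PFS.

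**1. Direction.** Take one patient who fails by dying without a RECIST progression. If the death counts, the Kaplan-Meier estimate is multiplied at that time by (1 − 1/n), with n the number at risk. If the patient is censored, that factor is missing. From the time of that failure onward, the curve is never lower than if the death had counted. The same holds if the patient is censored at the last scan instead. The error therefore goes one way.

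**2. Chance of at least one such failure among 20.** If each patient has an assumed risk r, the chance is 1 − (1 − r)^20: 64% at r = 5%, 88% at 10% and 99% at 20%.

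**3. Illustrative size, uncounted failures spread evenly over time.** Inputs: a true median of 6 months, borrowed from the background figure in section 1.1 as a convenient scale; exponential failure; and a share q of failures left uncounted. The documents do not give q. The hazard falls from ln 2/6 to (1 − q) × ln 2/6, so the reported median is 6/(1 − q) and the 6-month rate is 0.5^(1 − q).

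| q (assumed) | Reported median, months | 6-month rate |
|---|---|---|
| 0 | 6.0 | 50% |
| 5% | 6.3 | 52% |
| 10% | 6.7 | 54% |
| 20% | 7.5 | 57% |
| 30% | 8.6 | 62% |
| 40% | 10.0 | 66% |

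**4. Illustrative size, uncounted failures all before the first scan.** The first scheduled assessment is at 9 weeks (section 2.4). With a 26-week median, 1 − 0.5^(9/26) = 21% of patients fail before then, about 4 of 20. I used 4,000 simulated trials of 20 patients, with progression dated at the next 9-weekly scan, follow-up cut at 104 weeks, and an assumed share of the failures before week 9 left uncounted. The simulation keeps 9-weekly scans throughout, whereas section 5.12 moves to 12-weekly in year 2.

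| Share of failures before week 9 uncounted | Mean number of 20 | Typical median, all counted → as written (weeks) | Mean of medians, all counted → as written (weeks) |
|---|---|---|---|
| 25% | 1.1 | 27 → 27 | 29 → 32 |
| 50% | 2.2 | 27 → 36 | 30 → 35 |
| 100% | 4.3 | 27 → 36 | 30 → 40 |

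The typical median moves in 9-week steps because progression is dated at scans. With about one patient missed it does not move; with about two it moves by a full scan interval.

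**5. The 6-week rule.** On the same scale, 1 − 0.5^(6/26) = 15% of patients, about 3 of 20, fail before week 6. If section 4.8 is applied to PFS, those who stop treatment for that reason leave the analysis whatever section 2.2.1 says. Adding death to the definition would not bring them back.

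**The case against.** The strongest reply is that the endpoint is called progression-free survival, section 2.2.1 is a one-line objective, and any statistician would count deaths. The documents do not state that deaths will be censored. A reader might infer that overstatement is built into the results; it is not. It follows only if the definition is applied as written. That qualification stands, but it does not supply the missing event: the written definition is explicit, and the adjacent OS item shows that death was named where it was intended.

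Other stronger readings are tempting, and the documents do not support them:

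- **Section 4.5 as a second route around RECIST.** It says "Disease progression can also be confirmed histologically, cytologically, or surgically, or by physical examination or other clinical signs, per PI discretion". This follows a paragraph about patients who already have radiographic progression by RECIST 1.1 and await repeat imaging. Its natural meaning is confirmation of that progression, in which case a PFS date already exists. Only the bone-agent rule clearly supports the non-RECIST part of this point.
- **All early failures are lost.** Section 5.15 allows scans when clinically indicated, so some deteriorating patients will be scanned before week 9. Eligibility requires ECOG 0 or 1 and a life expectancy of at least 16 weeks, which makes very early deaths less likely. Section 4.8 is also a separate cause of early loss.
- **The result cannot be compared with the 6-month median in section 1.1.** That section does not say how its PFS was defined, and no comparison is planned.

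It is also fair that PFS is secondary, carries no hypothesis or threshold, and has no bearing on the Simon decision.

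**Conclusion.** The point holds. Section 2.2.1 omits death, nothing elsewhere restores it, and taken literally with section 9.3.2 it yields time to progression under the name PFS. The direction is certain once a patient dies without a RECIST progression: upward. The bone-agent rule, together with footnote 4, may add patients whom the protocol treats as progressed but who have no RECIST date.

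The size is not known. The range of 6.7 to 8.6 months against a true 6 months rests on exponential failure and on an assumed 10% to 30% of failures uncounted, neither taken from the documents. If only about 1 of 20 is missed, the effect may be negligible: the typical simulated median stays at 27 weeks, although the mean of the medians rises by about 3. The correction should be made because it is cheap and the ambiguity is avoidable, not because a large bias has been shown.

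**What to change.** - **Section 2.2.1:** define PFS as time from C1D1 to first RECIST 1.1 progression or death from any cause, whichever comes first. This also fixes the start date, which the present text leaves as an undated baseline.
- **Section 9.3.2:** state the censoring rule, including the censoring date for patients with no event and the handling of new anticancer therapy before progression.
- **Sensitivity analysis:** count clinical progression under the bone-agent rule, without RECIST progression, as an event on its date. Sections 4.3.1, 4.3.2 and footnote 4 should be reconciled so that it is clear how such patients are classified and followed for this endpoint.
- **Analysis set:** analyse PFS in all treated patients, so that the 6-week evaluability rule in section 4.8 does not remove the earliest failures.

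The cost is wording. Deaths before progression are already captured through safety reporting (sections 6.1.4 and 6.4.2) and through section 4.6. No extra patients, visits or scans are needed; imaging beyond the 30-day visit would add procedures and is not part of this proposal. The downside is that reported PFS may be slightly shorter.
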